⁸ In line with the explanation above, the in-person round includes an additional research question related to interviews with health care providers: Has provider knowledge of proper pneumonia diagnosis and treatment changed over the past three years? In the remote rounds, no interview is conducted with health care providers.

⁹ One and two councils were sampled from Mbeya and Songwe regions, respectively. In 2016, the Songwe region was created from the western part of Mbeya region. Two councils in Kagera region were excluded because the survey was piloted in those areas. Two councils from Arusha region were replaced at the request of the survey firm, EDI, due to the councils being located inside national parks, which would have presented significant logistical difficulties.

¹⁰ Councils were weighted according to the proportion of public health facilities in each council so that councils with a higher number of public health facilities would have a greater probability of selection.

¹¹ The list of active public health facilities at the dispensary, health center, and district hospital level was downloaded from MoHCDGEC's Health Facility Registry in January 2017.

¹² District hospitals were over-sampled since one of the survey objectives focused on the availability of electricity and oxygen at district hospitals.

¹³ Districts with fewer than seven dispensaries included all dispensaries.

This resulted in a total sample of 624 health facilities. The sample was comprised of 53 district hospitals, 50 health centers, and 521 dispensaries, out of a total of 61 district hospitals, 477 health centers, and 4,471 dispensaries in Tanzania (according to Tanzanian Government Open Data information from July 2016). When possible, the same facilities were surveyed in each round of data collection to allow outcomes within each facility to be compared over time.

Phase II

For the eight rounds of data collection in Phase II, we selected a sub-set of approximately 250 health facilities from the 2017 Phase I sample of public health facilities using a geographically stratified randomization approach. The sampling process was as follows:

1. Ran power calculations and determined the need to select 10 regions.
2. Randomly selected one region from each of the eight geopolitical zone in Tanzania,¹⁴ for a total of eight regions selected.

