3. Purposively selected the Dar es Salaam and Mwanza regions to ensure population and urban representation, resulting a total of 10 regions selected.

In the 2017 study, there were an average of 25 facilities sampled per region, across three districts. All facilities from the 2017 Phase I sample in these ten regions were included in our Phase II sample, resulting in a sample size of 251 health facilities. This approach will allow outcomes to be compared over time within each facility from 2017 to 2021 and allows to detect a change of 8.51 percentage points.

If a facility is permanently closed over the course of Phase II data collection, a facility of the same category (district hospital, health center, dispensary) will be randomly selected from the same district to serve as a replacement facility in the sample.

III. Data Collection

Round 1 of Phase I was conducted in March 2017,¹⁵ Round 2 was conducted in July 2017, and Round 3 was conducted November 2017.

Data collection for the first remote round of Phase II will be conducted over 3 weeks from May 12, 2020 to June 8, 2020.

Data collection methods

The remote public health facility survey employs a CATI data collection method in which enumerators speak with respondents over the phone and record responses in a tablet as the responses are given. The

¹⁴ Geopolitical zones were defined as those used in the 2015/2016 Demographic and Health Survey (DHS) and 2017 Malaria Indicator Survey.

¹⁵ The first round of data collection in March 2017 was intended to serve as a baseline measure of Amox-DT availability, stocking, and dispensing before R4D-funded Amox-DT reached health facilities. However, since peds-Amox had already reached emergency stocking levels nation-wide, R4D and the MoHCDGEC agreed to start Amox-DT distribution upon its arrival in country in late 2016. The first shipment of R4D-administered Amox-DT reached MSD zonal stores on January 15, 2017 and began distribution to health facilities shortly thereafter.

survey is a structured interview that includes requests for respondents to conduct stock counts and carry out record reviews.

The survey is comprised of three questionnaires:

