
Stocking:
 
3. What are the stocking levels of peds-Amox in public health facilities?
 
4. Has the stocking of peds-Amox in public health facilities changed over the past 3 years? If so, by how much?
	
Primary:
 
% of facilities that experienced stock outs (one day or more without stock) of peds-Amox in the last 90 days
 
Secondary:
 
Mean number of days of current peds-Amox stock out
 
% of facilities that have resolved a stock out of Amox-DT in the last 90 days
 
Mean number of days of the most recent stock-out that has been resolved
 
Mean number of days since facility received most recent Amox-DT shipment
 
Additional metrics that provide context:
 
How the most recent stock out was resolved
 
% of facilities whose MSD Amox-DT order has not been filled

III. Analysis Description

Levels: Availability and Stocking

The primary research question we aim to answer with Phase II of this study is: What is the availability of peds-Amox in public health facilities? To answer this question, we will provide a mean peds-Amox availability estimate across all facilities in our sample, as described below. The mean stocking levels of peds-Amox in public health facilities will be reported the same way.

Survey Weights

For Phase I, we will calculate mean peds-Amox availability using facility-level observations weighted by the probability that a facility was selected from the overall full sample of facilities in Tanzania. Results will be reported with 95% confidence intervals. The probability will be calculated as: the inverse of the probability of a district being selected multiplied by the inverse of the probability of a facility being selected within a district. We construct these sample weights under the assumption that selection into the sample is endogenously related to the number of facilities in each region and district, and that distribution and usage are correlated to regional characteristics, some of which we cannot observe.

$$Weight_{Phase I} = \frac{1}{Pr(\text{district being selected}) * Pr(\text{facility being selected within a district})} \quad [Eq 1]$$

For Phase II outcomes, we will present outcomes weighted by Phase I weights multiplied by the inverse of being selected for this round:

$$Weight_{Phase II} = Weight_{Phase I} * \frac{1}{Pr(\text{facility being selected from Phase I sample})} \quad [Eq 2]$$

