Our aim is to explore how outcomes have changed within facilities, on average, as a result of three years of R4D's catalytic funding. We will use the bivariate fixed effects regression reported in [Eq 3a]. Standard errors will be clustered at the facility level. This model measures the change in an outcome within each facility over time and takes the mean across all facilities in the sample. In this specification, each facility has outcomes measured at two points in time – in other words, all of the outcomes are “paired.”

This model will be used to analyze outcomes for facilities which had data in both Phase I, Round 1 and Phase II, Round T , where T is the round of interest. The analysis will be repeated on every outcome metric listed in *Table 1*.

$$Y_{jt} = \beta_0 + \beta_1 R_j + \sum_{j=1}^N \beta_{2,j} \eta_j + \varepsilon_{jt} \quad [\text{Eq } 3a]$$

Y_{jt} is the value of the outcome variable for facility j in round $t=T$, where T is the round of interest. Y_{jt} will be one of the outcome metrics listed in the right column of *Table 1*; the regression will be run for all outcome metrics in the table. R_j is an indicator variable equal to 1 if the observation for facility j is from Phase II, Round T of data collection or 0 if the observation is from Phase I, Round 1 (the “baseline”). The coefficient on R_j , β_1 is our coefficient of interest. β_1 will report the mean effect of three or more years of R4D's catalytic funding on our outcomes of interest. $\sum_{j=1}^N \eta_j$ represents facility category (hospital, health center, or dispensary) fixed effects. This is a set of dummy variables for each facility category; one category will be omitted to prevent collinearity. ε_{jt} is the error term for facility j in round t . Subscripts specify the observation: j identifies the individual facility, and t denotes the data collection round. We elected to use facility type rather than individual facility characteristics as with the limited data collection, many facility characteristics are highly correlated with facility type.

Second Specification: Unpaired Outcomes Analysis

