Some facilities will have data on select outcomes in Phase I, Round 1 but lack the same data in Phase II, or vice versa. This may be due to, for example, a facility closing (in which case a replacement facility would be selected) or an inability to contact a facility. In the above specification, these facilities would drop out of the analysis since there is not two time periods for comparison – in other words, the observations are “unpaired.” To avoid losing these observations, we will run a second specification that includes these unpaired observations. In these instances, we will use a bivariate regression model with standard errors clustered at the facility level.

This model will compare the mean of the outcome for all Phase I facilities with the mean outcome for all Phase II facilities.

$$Y_{jt} = \beta_0 + \beta_1 R_j + \varepsilon_{jt} \quad [\text{Eq } 4a]$$

Y_{jt} is the value of the outcome variable for facility j in round $t=T$, where T is the round of interest. Y_{jt} will be one of the outcome metrics listed in the right column of *Table 1*; the regression will be run for all outcome metrics in the table. R_j is an indicator variable equal to 1 if the observation for facility j is from

Phase II, Round T of data collection or 0 if the observation is from Phase I, Round 1 (the “baseline”). The coefficient on R_j , β_1 is our coefficient of interest. β_1 will report the mean effect of three or more years of R4D’s catalytic funding on our outcomes of interest. ε_{jt} is the error term for facility j in round t . Subscripts specify the observation: j identifies the individual facility, and t denotes the data collection round.

The two methods provide two different measurements and the effect reported by the two will differ. It is important to note that there will be selection bias in paired outcomes analysis because it excludes facilities that have closed since the initial data collection in Phase I, Round 1 or facilities that we were unable to contact. However, both models are useful as they describe the effects of R4D’s program in different ways. The paired outcomes analysis examines changes in outcomes within facility over time, while the unpaired outcomes examines changes in average performance on outcomes for the whole sample over time.

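### The change regressions cluster standard errors only by facility, although facilities were sampled through districts and regions, so intervals and p-values are too optimistic if changes are correlated within those units

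*Combined protocol and SAP*

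**What the plan says.** Two regressions estimate the change (Analysis, III. Analysis Description). For the paired model, Eq 3a: "Standard errors will be clustered at the facility level". For the unpaired model, Eq 4a: "we will use a bivariate regression model with standard errors clustered at the facility level".

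The sample was built in stages (Research Methodology, II. Sampling Method). Phase I drew three districts in each mainland region, then facilities within those districts. For Phase II the team "Randomly selected one region from each of the eight geopolitical zone in Tanzania", added Dar es Salaam and Mwanza on purpose, and kept every Phase I facility in the ten regions, "resulting in a sample size of 251 health facilities". That section says the design "allows to detect a change of 8.51 percentage points". It also says the team "Ran power calculations and determined the need to select 10 regions". No inputs to the calculation are shown.

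Under Survey Weights, the plan assumes that "distribution and usage are correlated to regional characteristics, some of which we cannot observe". It uses this to justify the weights and not to choose a variance estimator. Level estimates are to carry 95% confidence intervals, with no variance method named.

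**The concern.** In a two-round comparison, clustering by facility allows for the two rows that one facility contributes. It treats all other pairs of facilities as independent, including those in the same district. The supply under study passes through zonal stores before it reaches facilities (Data Collection, footnote on Round 1), so a delivery or a shortage could move neighbouring facilities together. That would be correlation in the change, which is what drives the variance of β1.

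Nothing else in the plan repairs this:

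- Region and sampling-strata fixed effects appear only as robustness checks. They absorb differences in level, not changes specific to a region or district.
- Weights alter the point estimate and do not by themselves account for clustering.
- The Holm-Bonferroni correction deals with the number of tests, not with standard errors that are too small.

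At stake are the intervals and tests for the change in both primary outcomes, in every remote round.

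**Working it through.** **Inputs from the documents.** 251 facilities, 10 regions and three districts per region. This gives 251/10 = 25.1 facilities per region and 251/30 = 8.37 per district. Thirty districts is an inference from three per region; there would be slightly fewer if Mbeya or Songwe was drawn, since they had one and two councils. The stated detectable change is 8.51 percentage points.

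**Assumed.** ICC of the change of 0.02, 0.05 or 0.10, two-sided alpha 0.05 and 80% power. The documents give none of these for the 8.51 figure. The 0.05 convention appears only under Multiple Hypothesis Testing.

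**Step 1: can 8.51 be reproduced?** For a paired mean change, the detectable change is (1.960 + 0.842) × SD / √251. Setting this to 0.0851 gives SD = 0.0851 × 15.84 / 2.802 = 0.481. With equal availability p in both rounds and within-facility correlation r, SD² = 2p(1 − p)(1 − r).

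- No design effect: p = 0.70, r = 0.45 gives SD = √(2 × 0.21 × 0.55) = 0.481. This fits.
- With a design effect: p = 0.80, r = 0.50 gives SD = √(2 × 0.16 × 0.50) = 0.400. A design effect of (0.481/0.400)² = 1.45 then also fits, which corresponds to a region ICC of 0.45/24.1 = 0.019.
- An unpaired comparison of 251 with 251 gives about 10.8 to 12.4 points for baselines of 30% to 70%, and does not fit.

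The figure is therefore neither confirmed nor refuted.

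**Step 2: effect of ignoring clustering.** The design effect is DEFF = 1 + (m − 1) × ICC. The true size of a nominal 5% test that ignores it is 2 × [1 − Φ(1.96/√DEFF)]. If 8.51 contains no design effect, it becomes 8.51 × √DEFF. Worked example for district, ICC 0.05: DEFF = 1 + 7.37 × 0.05 = 1.37; 1.96/√1.37 = 1.675; size = 9.4%; detectable change = 8.51 × 1.170 = 10.0 points.

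| Correlated unit | Assumed ICC | DEFF | True type I error | Coverage of a 95% interval | 8.51 becomes |
|---|---|---|---|---|---|
| District (m = 8.37) | 0.02 | 1.15 | 6.7% | 93.3% | 9.1 |
| | 0.05 | 1.37 | 9.4% | 90.6% | 10.0 |
| | 0.10 | 1.74 | 13.7% | 86.3% | 11.2 |
| Region (m = 25.1) | 0.02 | 1.48 | 10.7% | 89.3% | 10.4 |
| | 0.05 | 2.21 | 18.7% | 81.3% | 12.6 |
| | 0.10 | 3.41 | 28.9% | 71.1% | 15.7 |

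The region rows apply only if inference extends beyond the ten regions. These figures use normal quantiles. With t quantiles on 9 degrees of freedom, the last three detectable changes become 11.6, 14.2 and 17.6.

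**Step 3: simulation check.** Paired changes were simulated for 10 regions of 25 facilities, 4,000 runs. The facility-clustered test rejected in 5.2% of runs with no ICC, in 11.0%, 18.5% and 28.3% at region ICC 0.02, 0.05 and 0.10, and in 9.5% and 13.5% at district-only ICC 0.05 and 0.10. This agrees with the formula. Region clustering with t on 9 degrees of freedom stayed between 4.3% and 5.8%. District clustering held about 5% when there was no region-level correlation, but rejected in 12.1% at region ICC 0.05.

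These calculations describe the paired change. They ignore unequal weights and any finite-population correction. Eq 4a has the same clustering rule, but its exact design effect depends on which Phase I facilities enter.

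**The case against.** **The size is assumed.** Every ICC here is a supposition. The plan's remark on regional characteristics concerns distribution and usage, and stable regional differences cancel in a paired contrast. This stands. A reader might infer that every interval in the study is too narrow; the documents support that only if the ICC of the change is positive. For the level estimates the variance method is simply not stated, which is a gap and not a demonstrated error.

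**The region figures may not apply.** The plan disclaims national representativeness for Phase II, and its preferred estimates are taken across the ten regions. For that target, region is a fixed stratum. The district rows are then the relevant ones, with an ICC net of region. This also stands, although Changes over Time describes the primary aim as understanding availability in Tanzania overall, so the target is ambiguous.

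**A concentrated shift would be visible.** A reader might infer that a supply shift in a few regions would pass as a clear national change. Summaries by region and Medical Stores Department zone, and re-runs without Dar es Salaam and Mwanza, would help to expose such a shift. They do not correct the p-values.

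**Clustering may be in the power calculation.** A reader might infer that 8.51 ignored clustering and is wrong. The calculation was used to choose a number of regions, and the figure fits inputs both with and without a design effect, so that inference is not supported. Nor does the Holm-Bonferroni step by itself show that the figure is too low: the full division of alpha applies only to the smallest p-value in a family, and whether the calculation allowed for it is not stated.

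None of this defends the clustering rule itself. Districts were sampled, and the variance for the change leaves them out.

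**Conclusion.** The point holds for the two change models. Their stated standard errors omit the sampled units above the facility and are too small whenever changes are positively correlated within districts, or within regions if conclusions reach past the ten regions. The omission is certain from the text; its size is not. Under the assumed ICCs, true type I error runs from about 7% to 14% for the ten-region target and from about 11% to 29% for wider inference.

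The 8.51-point figure is undocumented, not shown wrong. If it contains no design effect, the corresponding value is about 9.1 to 11.2 points (district) or 10.4 to 15.7 points (region) for ICC 0.02 to 0.10.

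**What to change.** 1. State the target population: the ten regions, or mainland Tanzania.
2. For the preferred ten-region estimates, replace facility clustering in Eq 3a and 4a with a survey-design variance: district as primary sampling unit, region as stratum, the sampling weights, and design degrees of freedom (about 30 − 10 = 20). Add a rule for any region with a single sampled council, which would arise if Mbeya was drawn.
3. Name the same variance for the 95% confidence intervals of the level estimates.
4. For any statement about Tanzania as a whole, add a sensitivity analysis clustered by region with a few-cluster method, such as a wild cluster bootstrap or t on clusters minus one. Note that only eight regions were random, one per zone, so zones must be collapsed as strata. Note too that the two purposive regions have no random selection probability; region clustering alone does not make the estimate national.
5. Recompute and restate the detectable change under the design actually analysed, with its power, alpha, baseline, within-facility correlation and ICC.

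The cost is some wording in the analysis plan, a few lines of Stata and a documented power calculation. No new data are needed. The downside is wider intervals and a less favourable stated detectable change.

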All regressions will be weighted using the weights described in the *Analysis, Levels: Availability and Stocking* section above. Regressions will be run both including and excluding Dar es Salaam and Mwanza to explore how the “purely randomly-selected” subsample differs from our “purposively-selected” subsample.

Our preferred measure of change in peds-Amox availability will be the mean effect as calculated across all 10 regions in our subsample using the survey weights.

IV. Robustness Checks

Purely Random Selection vs. Purposive Selection

As a further robustness check on selection, we will run the specifications above including an indicator variable S_j equal to 1 if facility was in one of the eight districts from the purely random sample and equal to 0 if the facility was in the purposively selected districts of Dar es Salaam and Mwanza. The coefficient of interest in this regression, coefficient β_3 , will measure if being in the purely randomly-selected sample has any influence on outcome measures as compared to being in the purposively-selected sample.

$$Y_{jt} = \beta_0 + \beta_1 R_j + \sum_{j=1}^N \beta_{2,j} \eta_j + \beta_3 S_j + \varepsilon_{jt} \quad [Eq\ 3b: Paired\ outcomes\ analysis]$$

$$Y_{jt} = \beta_0 + \beta_1 R_j + \beta_3 S_j + \varepsilon_{jt} \quad [Eq\ 4b: Unpaired\ outcomes\ analysis]$$

Health Facility Quality and Size

We hypothesize that the quality and size of a health facility would influence our outcome measures. However, the direction of the effect is ambiguous. For example, a larger health facility may have capacity to stock greater quantities of medications, but because it serves a larger number of referral patients it may also face a greater demand for those medications. Similarly, better quality health facilities may be better at ordering medicines from MSD and therefore receive more medicines; however, there could be a greater demand for services and medications at better quality facilities.

We will run the same models specified in the *Analysis* section but include facility-level variables collected in the survey instead of facility category fixed effects.

$$Y_{jt} = \beta_0 + \beta_1 R_j + \delta_{i,j} X_{i,j} + \varepsilon_{jt} \quad [Eq\ 3c: Paired\ outcomes\ analysis]$$

$$Y_{jt} = \beta_0 + \beta_1 R_j + \delta_{i,j} X_{i,j} + \varepsilon_{jt} \quad [Eq\ 4c: Unpaired\ outcomes\ analysis]$$

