In the equations above [Eq 3c] and [Eq 4c], X_i are facility-level variables intended to proxy for the quality and size of each facility. We will include the following variables as control variables in our model:

- Mean availability of all medication surveyed (taking the mean across binary availability indicators for each medication surveyed)
- Number of health care providers for children under 5
- If healthy facility has a functional stethoscope
- If health facility is connected to the electricity grid
- If healthy facility provides oxygen therapy

Fixed Effects

The primary paired outcomes analysis model [Eq 3a] includes facility category fixed effects. We will also report the results of running the model with alternate fixed effects:

1. Individual facility fixed effects
2. Region fixed effects – this specification will be done removing the weighting specified in the *Analysis* section.
3. Sampling strata fixed effects

Technical Challenges

I. Multiple Hypothesis Testing

To account for the large number of hypotheses being tested in the analysis, we will adjust our results for multiple hypothesis testing by using the Holm-Bonferroni correction. This correction imposes a more conservative threshold for statistical significance since standard cutoffs would likely result in a statistically significant outcome by chance alone (i.e., false positive). This ensures that statistically significant findings are more likely to reflect actual change rather than a false positive.¹⁶

The Holm-Bonferroni correction is an extension of the popular Bonferroni correction, which very simply adjusts the threshold for significance by a factor equal to the number of tests being conducted. Instead of adjusting by a constant factor for all tests, the Holm-Bonferroni correction makes a sequential step-wise adjustment by increasing the threshold of the most significant result by a factor equal to the total number

¹⁶ If we do multiple comparisons, the probability of a false positive is: $1-(1-a)^m$, where m is the number of tests and a is the significance level (set at 0.05 by convention). For example, if we were to ask seven questions from the same data at the 5% level of significance, we would increase the chance of finding at least one false positive from 5% (with one question) to about 30%.

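### Loss and replacement of facilities can bias both change models, but the plan warns of this only for the paired one and reads both coefficients as the programme effect

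*Combined protocol and SAP*

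**What the plan says.** Analysis, III. Analysis Description sets out two models for change since Phase I Round 1. The First Specification (Eq 3a) is used to "analyze outcomes for facilities which had data in both Phase I, Round 1 and Phase II", Round T. The Second Specification (Eq 4a) also takes in facilities with data at only one time, and compares the Phase I mean with the Phase II mean. In both, the coefficient on the round indicator is read as the mean effect of the funding.

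The Second Specification section then says "The two methods provide two different measurements and the effect reported by the two will differ" and that "there will be selection bias in paired outcomes analysis because it excludes facilities that have closed since the initial data collection", adding facilities that could not be contacted. It names no bias for Eq 4a, which it describes as showing change in the sample-wide average.

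Technical Challenges, II. Missing Data, says that permanently closed and uncontactable facilities are replaced at random by one of the same level and district. It states no replacement for temporary closures.

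On which result leads, the text before Robustness Checks says "Our preferred measure of change in peds-Amox availability will be the mean effect as calculated across all 10 regions". That settles regions and weights, not the model. The Fixed Effects paragraph under Robustness Checks calls Eq 3a the primary paired model. The footnote on the Holm procedure allows either model.

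**The concern.** A facility that has closed or cannot be reached has no follow-up value in either model. Eq 3a drops it from both rounds and estimates change among retained facilities. Eq 4a keeps its Phase I value and supplies a different facility's Phase II value, or none. Eq 4a therefore compares partly different facilities before and after, and learns nothing about how the lost ones changed.

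The plan brings in Eq 4a so that one-round observations are not discarded, and warns of bias only for Eq 3a. A reader may then take Eq 4a as the remedy, or take agreement or disagreement between the two as extra evidence on the effect. Questions 2 and 4 could end with two estimates and two significance calls, and no clear rule for which one answers the question.

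**Working it through.** **The plan's own figure.** Sampling Method, Phase II, gives 251 facilities and says the design "allows to detect a change of 8.51 percentage points". Power, baseline rate and within-facility correlation are not given, and the 0.05 level appears only in the multiplicity footnote. The figure therefore cannot be uniquely reproduced. Assuming two-sided 0.05, 80% power and a 50% baseline:

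- Independent samples of 251 per round: 12.4 points.
- Paired, 2.80 × √(2 × 0.25 × (1 − ρ)/251): 10.5, 8.8 and 6.9 points at ρ = 0.3, 0.5 and 0.7. A value of 8.51 needs ρ of about 0.54.

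So 8.51 is attainable with plausible paired inputs. It serves below only as a yardstick.

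**The gap between the models.** Let f be the weighted share lost, r1 and r2 the retained means at Phase I Round 1 and at Round T, l1 the lost facilities' mean at Phase I, l2 the mean they would have had at Round T, and s2 the replacements' mean at Round T. Use the same weights in both rounds.

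- Eq 3a = r2 − r1. In a balanced panel the facility-category terms do not alter this.
- Eq 4a with replacement = [(1 − f)r2 + f·s2] − [(1 − f)r1 + f·l1].
- Gap (Eq 4a − Eq 3a) = f × [(s2 − r2) − (l1 − r1)].
- The same gap, split = f × [(l2 − l1) − (r2 − r1)] + f × (s2 − l2).
- With no replacement, the gap = f × (r1 − l1).

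In the split form, the first term is a real difference in change and the second is the replacement difference. Since l2 is never observed, the data cannot separate them.

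**Check without loss.** On a simulated panel of 251, Eq 3a and Eq 4a both gave 11.95 points unweighted and both gave 10.75 with common weights. With round-specific weights (Eq 1 for Phase I, Eq 2 for Phase II) they gave 10.81 and 10.74, so a small gap can arise from weights alone.

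**Checks with loss.** Assumed levels: retained facilities 60% then 75%, lost facilities 40% at baseline. At f = 0.20 the Phase I mean is 0.8 × 60 + 0.2 × 40 = 56. Eq 3a is 15 throughout.

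| Scenario at f = 0.20 | Eq 4a | True whole-sample change |
|---|---|---|
| All change +15, replacements like the retained (75) | 75 − 56 = 19 | 15 |
| All change +15, replacements like the lost (55) | (60 + 11) − 56 = 15 | 15 |
| Lost change 0, replacements like the lost (40) | (60 + 8) − 56 = 12 | 0.8 × 15 = 12 |

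Simulation (4,000 replicates) at 10%, 20% and 30% loss gave 17.0, 19.0 and 20.9 for the first row. For the third row it gave 13.5, 12.0 and 10.6, against true values of 13.5, 12.0 and 10.5. In the first row Eq 4a is wrong and Eq 3a right. In the third row Eq 4a is right for the whole sample and Eq 3a carries the selection bias that the plan describes.

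**Size in the first scenario, f × (s2 − l2):**

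| Share lost | 10-point difference | 20-point difference |
|---|---|---|
| 5% | 0.5 | 1.0 |
| 10% | 1.0 | 2.0 |
| 20% | 2.0 | 4.0 |
| 30% | 3.0 | 6.0 |
| 154/251 = 61% | 6.1 | 12.3 |

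The last row is an outer bound on non-contact. It counts facilities without freshly collected phone numbers (251 − 97 = 154) and is not a forecast of loss.

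**The case against.** The strongest defence is that the plan never says Eq 4a is unbiased. It states that the models measure different things, gives each a description, and concedes in Changes over Time that causality cannot be definitively claimed. Replacements are matched on level and district, which limits composition differences. The only loss with no stated replacement is temporary closure. The one count given is two facilities in Phase I Round 2, or 2/624 = 0.3%. With a 20-point difference and no replacement that shifts Eq 4a by about 0.06 points. Eq 4c adds facility covariates, and imputation is allowed if missingness is unexpectedly high.

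Much of this stands. A reader might infer that the plan declares Eq 4a free of selection bias, but that is drawn from silence. A reader might also infer that the gap is always a composition artefact and that Eq 4a is the worse estimate. The third scenario above shows otherwise.

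The defence does not cover the rest. Matching on level and district is not matching on stock. A replacement must itself be open and reachable, so it may resemble retained facilities more than lost ones. The alternate fixed effects are specified for Eq 3a only. Eq 4c adjusts for mean availability of all surveyed medicines, which on its face includes the outcome drug. Imputation is optional. No comparison of lost, retained and replacement facilities is planned.

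**Conclusion.** The point holds in a limited form. Loss and replacement can bias either model. The plan says so for Eq 3a only, while reading both coefficients as the programme effect. The gap between them is not independent evidence of effect, and its two components cannot be told apart from the data.

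If all facilities change equally, replacements resemble the retained and lost facilities were 10 to 20 points lower at baseline, a 10 to 20% loss moves Eq 4a by +1 to +4 points. That is 1/8.51 = 12% to 4/8.51 = 47% of the stated detectable change. Loss share, level difference and direction are all assumed. The sign reverses if lost facilities were better stocked, and the shift vanishes if replacements resemble the lost and all change equally. At 20% loss, a difference of 8.51/0.20 = 42.6 points would be needed to produce the full 8.51.

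A reader might also infer that no lead model exists. The documents support only an ambiguity, since calling Eq 3a the primary paired model could mean primary overall or primary among the paired variants.

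**What to change.** 1. In the Second Specification section, state that loss and replacement can bias both models. Give the target and the assumption of each, and say that their gap is not independent evidence of effect.
2. Where the preferred measure of change is defined, name the model that leads for questions 2 and 4.
3. Report Eq 3a with its weights multiplied by the inverse probability of being reached in Round T. Model that probability on Phase I Round 1 availability and stock-out status, facility level and region. Note that this removes bias only as far as those variables predict loss. A difference in change that remains after the adjustment is not corrected.
4. Report Phase I outcomes of lost against retained facilities, and Phase II outcomes of replacement against retained facilities. Run Eq 4a on the paired facilities with one fixed weight per facility, to show how much of any gap comes from facilities seen once and how much from weighting.
5. Declare whether permanently closed facilities belong to the target population. Closure may itself be a real change in availability, so this is a choice of target for the sponsor to state in advance.

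The cost is plan wording, one response model per round using Phase I data already held, and slightly wider intervals from the response weights.
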